- -Adults 18 years or older who complain of facial pain or pressure
- ≥ 3 months of symptoms duration (can be intermittent)
- Pain/pressure VAS score ≥ 5

Exclusion Criteria

- Sinonasal surgery within the last 3 months
- Grade 3-4 polyps
- Upper respiratory illness within last 2 weeks
- Topical decongestant use in last week
- Current nasal crusting or ulceration on rhinoscopy
- History of severe nose bleeding within last 3 months
- Known pregnancy
- Allergic sensitivity to silicone or any other component of device
- Inability to read and understand English
- Inability to perform treatment due to underlying medical condition

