5.0 Number of Subjects

Aim 1, exhaled NO: We anticipate 10 healthy control subjects for the exhaled NO portion of the study.

Aim 2, ETD: This is a pilot study. The anticipated ETD study population is 30 subjects.

Aim 3, Facial pain/pressure: This is a pilot study. The anticipated facial pain/pressure study population is 30 subjects.

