6.0 Setting

Research will be conducted at the Medical University of South Carolina. Potential participant screening for all subjects across all aims, as well as baseline evaluations, will occur in the outpatient ENT clinics. For AIM 2, the 6-week post treatment assessment will take place in the outpatient ENT clinics. For AIM 3, follow-up measures will be collected remotely using REDCap at 2 and 4 weeks.

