8.1 Withdrawal

At any point during the study, a subject may withdraw from the study.

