10.0 Data Management

All analyses and graphs will be performed with SPSS 24.0, Sample Power 3.0, and Sigma Plot 10.0 (SPSS, Chicago, IL.). Disease information and demographic variables, such as age, gender, race, quality of life (QOL) scores, and VAS scores will be summarized using frequencies, means, and standard deviation as appropriate. Aim 1 nasal NO metrics will be compared between baseline vs 10 seconds and baseline vs 3 minutes. Aim 2 metrics (ETDQ-7, ETD VAS and tympanogram) will be compared between baseline and 6 weeks. Aim 3 metrics (VAS, BPI-SF, MCQ-SF) will be compared between baseline vs 2 weeks and baseline vs 4 weeks. Categorical variables will be compared using Chi Square or McNemar's test. Continuous variables will be compared using One-Way ANOVA with repeated measures follow by post-hoc analysis. Data regarding safety and patient satisfaction will be summarized for each time point. A p-value ≤ 0.05 will be considered statistically significant. Due to the exploratory nature of this study, no p-value correction (ie Bonferroni) will be applied.

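### Aim 3: classical repeated-measures ANOVA excludes any patient who misses one remote questionnaire, and the completers' change overstates benefit if patients with less relief stop replying

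*Combined protocol and SAP*

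**What the plan says.** Section 10.0 gives one method for all continuous outcomes: "Continuous variables will be compared using One-Way ANOVA with repeated measures follow by post-hoc analysis". It sets the Aim 3 comparisons as follows: "Aim 3 metrics (VAS, BPI-SF, MCQ-SF) will be compared between baseline vs 2 weeks and baseline vs 4 weeks". It adds that "A p-value ≤ 0.05 will be considered statistically significant".

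On follow-up, Section 6.0 states: "For AIM 3, follow-up measures will be collected remotely using REDCap at 2 and 4 weeks". Section 8.1 states: "At any point during the study, a subject may withdraw from the study". Section 5.0 gives the size: "This is a pilot study. The anticipated facial pain/pressure study population is 30 subjects".

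The Section 9.1 schedule labels week 2 the primary and week 4 the secondary timepoint for Aim 3. Section 3.0 puts the 4 weeks of home use and both questionnaires under its primary-timepoint label. These two places need to be reconciled.

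The plan defines no analysis set, missing-data rule, dropout allowance, replacement rule or sensitivity analysis. The software is given ("All analyses and graphs will be performed with SPSS 24.0, Sample Power 3.0, and Sigma Plot 10.0"), but not the SPSS procedure.

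**The concern.** Classical one-way repeated-measures ANOVA compares levels within subjects and needs a value at every level. With three levels, a patient who lacks either follow-up value leaves the whole analysis of that outcome. Someone who answered at week 2 but not at week 4 is lost from the week-2 comparison too, although both values it needs were collected.

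Two things are at stake. The first is precision, since a group of 30 has few patients to spare. The second is bias. The study has a single arm, so the estimate is a plain change from baseline and no control group shares the same losses. If replying depends on how much relief a patient felt, the completers are a selected group.

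**Working it through.** The plan states no SD, effect size, power or dropout rate, so it has no figure of its own to reproduce. From the documents come n = 30, three assessments and the ANOVA. Everything else below is assumed.

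**1. Patients left.** With return probability r per follow-up and independent misses, expected complete cases = 30 × r².

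| Return per visit | Calculation | Complete cases |
|---|---|---|
| 95% | 30 × 0.95² | 27.1 |
| 90% | 30 × 0.90² | 24.3 |
| 85% | 30 × 0.85² | 21.7 |
| 80% | 30 × 0.80² | 19.2 |

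Even at 95%, the chance of losing at least one patient is 1 − 0.95⁶⁰ = 0.95. If only week 4 is ever missed, the count is 30 × r: 27.0, 25.5 and 24.0 at 90%, 85% and 80%.

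**2. Bias by hand.** Suppose half the patients improve by 3 points, half by 0, and a share d of the non-improvers stops replying. The true mean change is −1.50. The completers' mean is −1.5 / (0.5 + 0.5 × (1 − d)).
- d = 0.2: −1.5 / 0.90 = −1.67, overstated by 0.17.
- d = 0.5: −1.5 / 0.75 = −2.00, overstated by 0.50.

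**3. Bias by simulation, dropout driven by observed scores.** Settings: 4,000 trials of n = 30, VAS SD 2, correlation 0.6 and no true change. All week-2 scores are observed. Week-4 non-return is logistic in the week-2 change.

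| Non-return at average response | Log-odds per point less improvement | Completers, week 2 | Completers, week 4 |
|---|---|---|---|
| 15% | 0.5 | −0.26 | −0.13 |
| 15% | 0.8 | −0.43 | −0.21 |
| 25% | 0.5 | −0.39 | −0.20 |
| 25% | 0.8 | −0.59 | −0.30 |

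The first column is not the overall dropout rate. Overall week-4 missingness runs from 18% in the first row to 31% in the last. Estimates that use every observed visit are within 0.01 of zero in all four rows.

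For scale, the SD of a change score is √(2 × 2² × (1 − 0.6)) = 1.79, so its standard error at n = 30 is 1.79 / √30 = 0.33.

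**4. Same settings, dropout driven by the unseen week-4 score.** At week 4 completers show −0.26 to −0.59, and the likelihood estimate from all observed data shows −0.18 to −0.44. About 71% to 74% of the bias remains.

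**5. Random missingness.** Completers are unbiased, and only patients are lost.

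**The case against.** *Listwise deletion is not written in the plan.* This is true. A reader might infer that the plan prescribes it, but exclusion follows from the classical form of the named method. Section 10.0 also frames Aim 3 as two contrasts with baseline. If these were run as separate paired comparisons, a patient with a week-2 reply would stay in the week-2 contrast. In the simulation of step 3 the week-2 bias would then vanish without a mixed model, leaving 0.13 to 0.30 at week 4. The text does not say the analysis will be run that way.

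*Who drops out is not known.* This stands. A reader might infer that the completers' result will favour the device. The documents do not support that, because they give no dropout rate or pattern, and the bias reverses if improved patients are the ones who stop replying. Weekly compliance calls (Section 9.0), $50 per visit up to $150 for this group (Section 15.0) and a 4-week follow-up may keep losses low. None of these says how a missing reply is analysed.

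*The week-4 bias is modest.* Every week-4 figure in step 3 is below one standard error (0.33). The largest week-2 figure, 0.59, is 0.59 / 0.33 = 1.8 standard errors.

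*This is an exploratory single-arm pilot.* Entry requires "Pain/pressure VAS score ≥ 5", so change from baseline is also open to regression to the mean, which no missing-data method repairs. That limits the weight of the point. Section 1.0 nevertheless sets efficacy as an aim, and Section 10.0 sets a significance threshold.

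*Aim 1.* A reader might extend the point to nitric oxide, with one failed reading removing 1 of 10 subjects. The documents do not support this: readings are taken in clinic with rest between trials, and nothing prevents repeating a failed one.

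**Conclusion.** The point holds for Aim 3. The named method, in its classical form, discards observed data from any patient with one missing questionnaire, and nothing in the plan offsets this. The loss of patients follows from arithmetic once a return rate is assumed.

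The bias towards benefit is conditional on patients with less relief being the ones who stop replying. The sizes of 0.26 to 0.59 points at week 2 and 0.13 to 0.30 at week 4 rest on SD 2, correlation 0.6 and 18% to 31% week-4 missingness driven by week-2 response. They illustrate what could happen and do not predict this study's result.

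A reader might also infer that a mixed model cures the problem. It does so only when dropout depends on observed scores. Otherwise it reduces the bias and leaves most of it. The change is worth making because it is cheap and uses data already collected.

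**What to change.** For Aim 3, replace the ANOVA sentence in Section 10.0 with wording such as:

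> Aim 3 continuous outcomes will be analysed with a linear mixed model for repeated measures (SPSS MIXED, REML, visit as fixed effect, unstructured covariance) using every observed visit. Change from baseline with its 95% confidence interval will be reported at each follow-up.

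Then add:
- the number missing at each visit, with the baseline and week-2 scores of those missing;
- a sensitivity analysis that sets missing follow-up to no change from baseline.

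The sensitivity analysis is a check and not a worst case. It roughly multiplies the completers' change by the share who replied. In the most extreme setting of step 4 that is 0.59 × 0.69 = 0.41 (0.69 being 1 − 0.31), so a patient who worsened and left is still counted too favourably.

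Cost: a change of SAP wording and a little more analysis work, in a package the plan already names. Visits, patient numbers and device use do not change.

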9.0 Study Design / Methods

This study is designed as a pilot study.

Data will be collected by the study investigators as well as the subjects themselves throughout the entirety of the study. The data will consist of answers from subjects for questionnaires asked by the clinicians as well as self-reported answers from the subjects.

Safety will be monitored throughout the study based on monitoring of adverse events, performing nasal, measuring vital signs (i.e. blood pressure, pulse) and weight, and through collection of concomitant medication information.

The period of observation for collection of non-serious adverse events extends from the time the subject gives informed consent until completion of the End-of-study visit or Early Termination Visit. Serious adverse events (SAE) will be reported from the time of informed consent through 30 days after the last use of the SinuSonic. Adverse event data listings will be reviewed by SinuSonic at regular intervals throughout the study. In

addition, SinuSonic will be alerted of Adverse Events of interest via automated emails programmed in the EDC system. Patient compliance will be assessed via weekly phone calls from study coordinator.

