9.1 Schedule of Events

Aim 1: NO in N=10 controls	Screening and baseline assessment
Day	0
Informed consent	X
Inclusion/exclusion criteria	X
Medical history	X
Rhinology, otoscopy	X
Vital signs	X
Exhaled nasalNO at 30 seconds and 5 min	X

Aim 2: ETD efficacy in N=30 patients	Screening and baseline assessment	Primary timepoint for outcomes
Week	0	6 + 1
Informed consent	X	
Inclusion/exclusion criteria	X	
Medical history	X	
Rhinology, otoscopy	X	X
Vital signs	X	
Distribution of Sinusonic	X	X
ETDQ-7	X	X
ETD VAS questionnaire	X	X
Tympanogram	X	X

Aim 3: Facial pain/pressure in N=30 patients	Screening and baseline assessment	Primary timepoint for outcomes	Secondary timepoint for outcomes
Week	0	2	4
Informed consent	X		
Inclusion/exclusion criteria	X		
Medical history	X		
Rhinology, otoscopy	X		

Vital signs	X		
Distribution of Sinusonic	X		
Pain/pressure VAS	X	X	X
BPI-SF	X	X	X
MPQ-SF	X	X	X

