Ear pressure	◆—————◆
Feeling that ears are clogged	◆—————◆
Cracking/popping of ears	◆—————◆
Muffled hearing	◆—————◆
Tinnitus (noise in ears)	◆—————◆
OVERALL ASSESSMENT OF EAR and EUSTACHIAN TUBE PROBLEMS	◆—————◆

BASELINE ETDQ-7

Next to each question, circle the number that best describes how you feel.

During the past 1 month, how much of a problem was each of the following?	No problem		Moderate Problem			Severe Problem	
Pressure in the ears?	1	2	3	4	5	6	7
Pain in the ears?	1	2	3	4	5	6	7
A feeling that your ears are clogged or "under water"?	1	2	3	4	5	6	7
Ear problems when you have a cold or sinusitis?	1	2	3	4	5	6	7
Crackling or popping sounds in the ears?	1	2	3	4	5	6	7
Ringing in the ears?	1	2	3	4	5	6	7
A feeling that your hearing is muffled?	1	2	3	4	5	6	7

Do you get these symptoms in one ear only or both ears?

Left ear only

Right ear only

Both ears

INCLUSION CRITERIA (all must be yes):

Does patient have ETD sx for ≥ 6 mos? Yes No

Is ETDQ-7 score ≥ 3 ? Yes No

Does patient have ≥ 3 ETD symptoms above? Yes No

AIM 2, ETD: Follow Up Questionnaire 5 minutes**FOLLOW UP ETD VAS 5 MINUTES**

OVER THE LAST FEW MINUTES, HOW TROUBLESOME HAVE THE FOLLOWING SYMPTOMS BEEN? PLEASE PLACE A MARK ON THE LINE.	
	Not troublesome Worst thinkable/troublesome
Ear pressure	◆—————◆
Feeling that ears are clogged	◆—————◆
Cracking/popping of ears	◆—————◆
Muffled hearing	◆—————◆
Tinnitus (noise in ears)	◆—————◆
OVERALL ASSESSMENT OF EAR and EUSTACHIAN TUBE PROBLEMS	◆—————◆

AIM 2, ETD: 6-Week Follow Up Questionnaires

Objective Evaluation			
Rhinoscopy:			
Bleeding:	None	Yes	
Crusting:	None	Yes	
Otoscopy:	 Normal	 Retracted no effusion	 Effusion
Valsalva:	 Successful	 Not successful	
Tympanogram type:	A	B	C

OVER THE LAST FEW MINUTES, HOW TROUBLESOME HAVE THE FOLLOWING SYMPTOMS BEEN? PLEASE PLACE A MARK ON THE LINE.		
	Not troublesome	Worst thinkable/troublesome
Ear pressure		
Feeling that ears are clogged		
Cracking/popping of ears		
Muffled hearing		
Tinnitus (noise in ears)		
OVERALL ASSESSMENT OF EAR and EUSTACHIAN TUBE PROBLEMS		

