6 WEEK ETDQ-7

Next to each question, circle the number that best describes how you feel.

During the past 1 month , how much of a problem was each of the following?	No problem		Moderate Problem			Severe Problem	
	1	2	3	4	5	6	7
Pressure in the ears?	1	2	3	4	5	6	7
Pain in the ears?	1	2	3	4	5	6	7
A feeling that your ears are clogged or "under water"?	1	2	3	4	5	6	7
Ear problems when you have a cold or sinusitis?	1	2	3	4	5	6	7
Crackling or popping sounds in the ears?	1	2	3	4	5	6	7
Ringing in the ears?	1	2	3	4	5	6	7
A feeling that your hearing is muffled?	1	2	3	4	5	6	7

Do you get these symptoms in one ear only or both ears?

Left ear only

Right ear only

Both ears

Change in eustachian tube symptoms and use of device

Please rate changes in your nasal symptoms and use of device.

Symptom	None	Mild	Moderate	High
Improvement in ear pressure	0	1	2	3
Improvement in ear clogging	0	1	2	3
Improvement in cracking/popping of ears	0	1	2	3
Improvement in muffled hearing	0	1	2	3
Improvement in tinnitus (noise in ears)	0	1	2	3
Improvement in ear pain	0	1	2	3
Improvement in ear problems with cold or sinus infection	0	1	2	3
Overall improvement in ear symptoms	0	1	2	3
Tolerability				
Pain with use of device	None	Mild	Moderate	Severe
Comfort and ease of use	Poor	Low	Moderate	High
Bleeding:	Yes	No		

Week 6 patient satisfaction

Would you use device again? Yes No

Would you recommend device to others? Yes No

AIM 3, SINUS PAIN/PRESSURE: Baseline Medical History and exam**SinuSonic Study****PI: [name]**

Subject ID#: _____ Subjects Initials: _____

DEMOGRAPHIC AND CLINICAL VARIABLES (If not previously collected):

Age at enrollment (years):

--	--

Gender: Male Female

What is/was your profession (current/retired)? _____

LANGUAGE, ETHNICITY, RACE, MARITAL STATUS**Please mark one of the following categories which describes your native language:**

- ☐ American English
- ☐ Other: please specify _____

Please mark one of the following categories which describes your ethnicity:

- ☐ Not Hispanic or Latino
- ☐ Hispanic or Latino

Please mark one or more of the following categories which describes your race:

- ☐ American Indian or Alaska Native
- ☐ Asian
- ☐ Black or African American
- ☐ Native Hawaiian or Other Pacific Islander
- ☐ White
- ☐ Other

SMOKING HISTORY**1. Do you currently smoke tobacco products? Yes No (If No please go to question 2)**

How many tobacco products do you use in a day? _____ Singles Packs

CURRENT MEDICATION USAGE

- | | | |

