G. Hot-Burning:	None (0)	Mild (1)	Moderate (2)	Severe (3)
H. Aching:	None (0)	Mild (1)	Moderate (2)	Severe (3)
I. Heavy:	None (0)	Mild (1)	Moderate (2)	Severe (3)
J. Tender:	None (0)	Mild (1)	Moderate (2)	Severe (3)
K. Splitting:	None (0)	Mild (1)	Moderate (2)	Severe (3)
L. Tiring-Exhausting:	None (0)	Mild (1)	Moderate (2)	Severe (3)
M. Sickening:	None (0)	Mild (1)	Moderate (2)	Severe (3)
N. Fearful:	None (0)	Mild (1)	Moderate (2)	Severe (3)
O. Punishing-Cruel:	None (0)	Mild (1)	Moderate (2)	Severe (3)

- 2) Please rate your **SINUS or facial** pain by circling the one number that tells how much pain you have **RIGHT NOW**.

0	1	2	3	4	5	6	7	8	9	10
No Pain										Pain as bad as you can imagine

- 3) Evaluate overall intensity of total pain experience. Please limit yourself to a description of the pain in your **SINUS area or face** only.
Place a check
mark (✓) in the appropriate column:

Evaluate		
0	No pain	
1	Mild	
2	Discomforting	
3	Distressing	
4	Horrible	
5	Excruciating	

AIM 3, SINUS PAIN/PRESSURE: Immediate (5 minute) Questionnaire

PATIENT QUESTIONS	
AFTER USING THE DEVICE, HOW WOULD YOU RATE YOUR SINUS OR FACIAL PAIN/PRESSURE?	
	None Worst possible
Sinus or facial pain/pressure	◆—————◆

AIM 3, SINUS PAIN/PRESSURE: 2 week Questionnaire

PATIENT QUESTIONS	
OVER THE LAST WEEK, HOW WOULD YOU RATE YOUR AVERAGE SINUS OR FACIAL PAIN/PRESSURE?	
	None Worst
	possible
Sinus or facial pain/pressure	◆—————◆

IMMEDIATELY AFTER USING THE DEVICE, HOW WOULD YOU RATE YOUR SINUS OR FACIAL PAIN/PRESSURE?	
	None Worst
	possible
Sinus or facial pain/pressure	◆—————◆

2 WEEK: Brief Pain Inventory-Short Form (BPI-SF)

2. Please rate your pain by circling the one number that best describes your pain at its worst in the last week.

0	1	2	3	4	5	6	7	8	9	10
No pain									Pain as bad as you can imagine	

3. Please rate your pain by circling the one number that best describes your pain at its least in the last week.

0	1	2	3	4	5	6	7	8	9	10
No pain									Pain as bad as you can imagine	

4. Please rate your pain by circling the one number that best describes your pain on average.

0	1	2	3	4	5	6	7	8	9	10
No pain									Pain as bad as you can imagine	

5. Please rate your pain by circling the one number that tells how much pain you have right now.

0	1	2	3	4	5	6	7	8	9	10
No pain									Pain as bad as you can imagine	

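### In Aims 2 and 3, patients who withdraw before the first follow-up form give no solicited device-pain, bleeding or satisfaction answer, and section 10.0 plans no per-patient safety summary that would include them

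*Combined protocol and SAP*

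**What the plan says.** Section 1.0 makes safety an objective of Aims 2 and 3 alongside efficacy. Section 12.0 names pain from the device, to a degree not yet known, nose bleeds and nasal crusting as risks.

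The analysis of safety is one sentence in section 10.0: "Data regarding safety and patient satisfaction will be summarized for each time point". No denominator is given, nor a rule for patients without a form.

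The time points come from section 9.1. The table headed "Aim 2: ETD efficacy in N=30 patients" has weeks 0 and 6. The table headed "Aim 3: Facial pain/pressure in N=30 patients" has weeks 0, 2 and 4. Neither has an early-termination column.

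Non-serious adverse events are collected from consent "until completion of the End-of-study visit or Early Termination Visit" (section 9.0, repeated in sections 11.0 and 19.0). On leaving, section 8.1 says only: "At any point during the study, a subject may withdraw from the study".

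In the appendix, the Aim 2 week-6 form has a tolerability block with "Pain with use of device" and a yes/no bleeding item, followed by two satisfaction items. The Aim 3 week-2 and week-4 forms ask about device pain and bleeding, each on a four-level scale, and the same two satisfaction items. The forms completed after the first use in clinic are headed "FOLLOW UP ETD VAS 5 MINUTES" and "AIM 3, SINUS PAIN/PRESSURE: Immediate (5 minute) Questionnaire". Both hold symptom VAS lines and nothing on tolerability.

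**The concern.** A patient who finds the device painful, or who bleeds, has a reason to leave the study. If that happens before the first form that asks about pain and bleeding, the patient gives no solicited tolerability answer. A summary by time point then describes only those who stayed long enough to be asked. The missing answers are plausibly the unfavourable ones, so the percentages for device pain, bleeding, willingness to use the device again and willingness to recommend it may look better than the experience of everyone treated. With 30 subjects per aim, a few such losses change the result, and answers not obtained at withdrawal may not be recoverable later.

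**Working it through.** The plan states no safety rate, dropout rate or precision target, so there is no figure of its own to reproduce. The check has two parts.

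**1. Where the solicited answers come from**

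| Contact | Device pain | Bleeding | Satisfaction |
|---|---|---|---|
| Aim 2, 5 minutes after first use | no | no | no |
| Aim 2, week 6 | yes | yes/no item, plus rhinoscopy | yes |
| Aim 3, 5 minutes after first use | no | no | no |
| Aim 3, week 2 | yes | graded item | yes |
| Aim 3, week 4 | yes | graded item | yes |
| Early termination, both aims | no form | no form | no form |

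Section 9.0 also provides weekly calls by the coordinator, but their only stated purpose is compliance. Section 9.1 schedules no rhinoscopy after baseline in Aim 3, and section 6.0 makes its follow-up remote, so the questionnaire is the only scheduled source of bleeding data there.

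It follows that an Aim 2 patient who withdraws before week 6, or an Aim 3 patient who withdraws before week 2, contributes no solicited answer. An Aim 3 patient who leaves between weeks 2 and 4 has answered once and is missing only at week 4.

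**2. How far the form-based percentage could move**

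This is an illustration, not an estimate. Let e be the number truly affected among 30 treated, and d the number of affected patients who withdraw before the form. Assume that all unaffected patients return it and that only returned forms are counted.

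- True proportion: e/30.
- Form-based proportion: (e − d)/(30 − d).
- Shortfall: e/30 − (e − d)/(30 − d) = d(30 − e) / [30(30 − d)]. This is positive whenever d > 0 and e < 30, so under these assumptions the error always favours the device.

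The intervals below are exact (Clopper-Pearson) 95% limits. With 0 events in n, the upper limit is 1 − 0.025^(1/n).

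| e | d | Form-based result | 95% CI | All treated |
|---|---|---|---|---|
| 3 | 1 | 2/29 = 6.9% | 0.8 to 22.8% | 3/30 = 10.0% (2.1 to 26.5%) |
| 3 | 2 | 1/28 = 3.6% | 0.1 to 18.3% | as above |
| 3 | 3 | 0/27 = 0% | 0 to 12.8% | as above |
| 6 | 3 | 3/27 = 11.1% | 2.4 to 29.2% | 6/30 = 20.0% (7.7 to 38.6%) |
| 6 | 6 | 0/24 = 0% | 0 to 14.2% | as above |

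Check of the shortfall for e = 3, d = 1: 1 × 27 / (30 × 29) = 3.1 percentage points, which is 10.0 − 6.9.

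**The case against.** The strongest reply is that adverse-event collection does not depend on these forms. Section 19.0 requires every adverse event, whatever its seriousness or relation to the device, to be reported from consent to that patient's end of study, and followed until recovery or stabilisation, if need be after the last planned visit. Serious events are reported up to 30 days after last use. Pain in clinic or nosebleeds in week 1 fall inside that window. This stands. A reader might infer that early leavers vanish from the safety record altogether, and the documents do not support that.

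Second, stopping the device is not the same as leaving the study. Nothing says that a patient who stops using it stops completing forms, and the Aim 3 forms are completed remotely. This also stands, and it limits the gap to patients who withdraw from the study before their first follow-up form.

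Third, the schedule in section 9.1 is not exhaustive: it also omits adverse events, the weekly calls and the 5-minute questionnaires. Naming an Early Termination Visit in three sections suggests that an exit contact is intended. That is fair, but intent does not supply content. No section says what is asked at that visit, and no form exists for it.

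Fourth, section 10.0 does not say that early leavers are excluded; it is silent on the denominator. That is correct. But it also does not say whether adverse events enter the summary by time point, and it plans no incidence per treated patient. The adverse-event sections promise only that listings are reviewed. Nor can adverse-event reports replace the satisfaction answers.

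Fifth, the extreme rows of the table are worst cases. They need every affected patient to leave unasked, and the interval for 0/27 still contains 10%. Both remarks are right, and the table should be read with them in mind.

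**Conclusion.** The point holds in a limited form. In Aims 2 and 3 the solicited tolerability and satisfaction summary omits anyone who withdraws before week 6 or week 2 respectively. The Early Termination Visit that could catch these patients has neither schedule entry nor form, and section 10.0 defines no safety denominator and no per-patient adverse-event incidence. The documents do not support the stronger inference that such patients' pain or bleeding goes unrecorded, or that everyone who stops the device goes unasked.

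The direction of the bias depends on one assumption: that withdrawal is related to pain, bleeding or dissatisfaction. If it is unrelated, the loss costs precision but does not shift the expected percentages. The size cannot be known from the documents. Under the assumed 3 affected of 30, the form-based figure runs from 6.9% (one lost) to 0% (all three lost), against 10%. In an exploratory pilot this is not a fatal flaw. It should still be corrected, because safety is a stated aim and the correction is cheap.

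**What to change.** 1. Add each aim's own device-pain and bleeding items to its 5-minute form. The bleeding item should stay yes/no in Aim 2 and graded in Aim 3, so that neither aim ends up with two bleeding scales.
2. Add an Early Termination column to the Aim 2 and Aim 3 schedules. It would contain the existing tolerability and satisfaction items, the date of last use and the reason for stopping. These can be taken by phone, including on the weekly call already planned.
3. In section 10.0, keep the summary by time point and add a per-patient summary with all subjects who used the device at least once as denominator. It should give the worst device-pain grade, any bleeding (yes/no in both aims, plus worst grade in Aim 3), any adverse event, and discontinuation with its reason. Subjects with no solicited answer should be shown as a separate category and not counted as free of pain or bleeding.

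The cost is two items on each of two existing forms, one column in each of two schedules, and a short addition to section 10.0. No clinic visit is added. Patients and the coordinator have a few more items to complete, and the reported event rates may look slightly less favourable.
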